### **8.3 Primary Efficacy Endpoint(s) and Analyses**

#### **8.3.1 Primary Efficacy Endpoint(s)**

The primary endpoint is the proportion of subjects achieving at least a 75% reduction from Baseline in Eczema Area and Severity Index (EASI 75) at Week 16.

The corresponding statistical null hypotheses are that there is no difference between each of the risankizumab dose group (150 mg and 300 mg, respectively) and placebo group in the proportion of subjects achieving EASI 75 at Week 16.

#### **8.3.2 Handling of Missing Data for the Primary Efficacy Endpoint(s)**

Missing data will be handled using NRI method as the primary approach. MMRM and MI method will be used as the sensitivity analysis.

#### **8.3.3 Primary Efficacy Analysis**

Pairwise comparison of the primary endpoint of EASI 75 will be conducted between each risankizumab group versus the placebo group using the CMH test adjusting for the stratification factor of vIGA-AD categories.

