Study Population and Number of Subjects to be Enrolled:	
Approximately 155 adult and adolescent subjects who have moderate to severe AD and meet the study's eligibility criteria will be randomized for participation in this study. The study plans to enroll approximately 20% of subjects from sites in Japan.

Investigational Plan:	
This is a Phase 2, randomized, double-blind, placebo-controlled multicenter study to evaluate the safety and efficacy of risankizumab for the treatment of moderate to severe AD in adult and adolescent subjects with onset of symptoms at least 2 years before the Baseline Visit. The duration of the study will be up to 65 weeks and will include a screening period of up to 35 days, a 16-week double-blind treatment period (Period A), and a 36-week double-blind treatment period (Period B). The primary analysis will be performed when all subjects have completed Week 16.
 
Eligible subjects will be randomized at Baseline to receive risankizumab 150 mg, risankizumab 300 mg, or matching placebo (2:2:1, respectively) at Week 0 and Week 4 of Period A. In Period B, subjects in the placebo group will be re-randomized in a 1:1 ratio to receive either risankizumab 150 mg or 300 mg for the remainder of the study. Subjects originally randomized to risankizumab 150 mg or 300 mg in Period A will stay on their previously-assigned treatment through the end of the study. All subjects will receive risankizumab at the Week 16, Week 28, and Week 40 visits. The last visit to the study site will occur at Week 52. Subjects will have a final follow up call 20 weeks after the last dose administration.
 
During Period B, subjects with < EASI 50 response, as compared to Baseline, at the most recent prior and current scheduled visits will be allowed to begin approved concomitant rescue treatment after the assessments at the Week 24 visit and at any visit thereafter. Rescue treatment is limited to up to twice-daily application of topical corticosteroids.

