## 5.8 Randomization/Drug Assignment

---

Each subject will be assigned a unique identification number by the IRT at the screening visit. For subjects who rescreen, the identification number assigned by the IRT at the initial screening visit should be used. In addition, the IRT will assign a unique randomization number that will encode the subject's treatment group assignment according to the randomization schedule generated by the statistics department at AbbVie. At Baseline (Study Day 0), subjects who meet eligibility criteria will be randomized in a 2:2:1 ratio to risankizumab 150 mg (N = 62), risankizumab 300 mg (N = 62), or matching placebo (N = 31). Randomization will be stratified by baseline disease severity (moderate [vIGA-AD 3] versus severe [vIGA-AD 4]) and geographic region (Japan versus rest of world).

At Week 16, subjects in the placebo group will be re-randomized in a 1:1 ratio to receive either risankizumab 150 mg or 300 mg for the remainder of the study. Subjects originally randomized to the risankizumab 150 mg or 300 mg arms will stay on their previously-assigned treatment through the end of the study.

While the sponsor will be unblinded as part of the Week 16 analysis, the investigator, study site personnel, and the subject will remain blinded to each subject's treatment for the duration of the study.

To maintain the blind, the risankizumab PFS and placebo PFS provided for the study will be identical in appearance and number of syringes.

In the event of a medical emergency in which the investigator believes that knowledge of study drug treatment is required, reasonable efforts must be made to contact the AbbVie Emergency Contact prior to breaking the blind, as long as it does not compromise subject safety. However, if an urgent therapeutic intervention is necessary that warrants breaking the blind prior to contacting the AbbVie Emergency Contact, the investigator can directly access the IRT system to break the blind without AbbVie agreement.

The date and reason that the blind was broken must be recorded in the source documentation and eCRF, as applicable.

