### 7.3 Statistical Analyses for Efficacy

---

Pairwise comparison of the primary endpoint and the key secondary endpoints will be conducted between each risankizumab group (risankizumab 150 mg and 300 mg, respectively) versus the placebo group using the Cochran-Mantel-Haenszel (CMH) test, stratified by baseline disease severity (moderate [vIGA-AD 3] versus severe [vIGA-AD 4]). For the analysis of the primary endpoint and key secondary endpoints, non-responder imputation (NRI) with multiple imputation (MI) to handle missing data due to COVID-19 (NRI-C) will be used as the primary approach. The non-responder imputation with no special data handling for missing data due to COVID-19 (NRI-NC) approach, observed cases (OC) approach, and MI may be conducted as appropriate sensitivity analyses to handle missing values.

Efficacy data for subjects who switch to rescue medications will be imputed from the point of rescue using an NRI approach for the primary endpoint and key secondary endpoints.

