### 2.3 Treatment Assignment and Blinding

Each subject will be assigned a unique identification number by the IRT at the screening visit. Subjects who rescreen will use the same unique identification number from the initial screening visit. In addition, the IRT will assign a unique randomization number that will encode each subject's treatment group assignment according to the randomization schedule generated by the statistics department at AbbVie.

At the Baseline visit, subjects meeting eligibility criteria will be randomized in a 2:2:1 ratio to risankizumab 150 mg, risankizumab 300 mg, or matching placebo.

Randomization at Baseline will be stratified by baseline disease severity (moderate [vIGA-AD 3] vs. severe [vIGA-AD 4]) and geographic region (Japan vs. Rest of the World [RoW]).

At the Week 16 visit, subjects receiving placebo in Period A will be re-randomized in a 1:1 Ratio to receive either risankizumab 150 mg or risankizumab 300 mg through Week 52. Subjects originally randomized to risankizumab 150 mg or 300 mg in Period A will stay on their previously assigned treatment through Week 52. There is no stratification at the re-randomization at Week 16.

To maintain the blind, all risankizumab and placebo kits provided for the study will be identical in appearance. AbbVie personnel will remain blinded until the primary analysis at Week 16 is available. The study sites and subjects will remain blinded to treatment assignments for the entire duration of the study.

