#### **Analysis of Categorical Variables**

Categorical variables will be summarized by frequencies and percentage by each treatment group. Pairwise comparison of each risankizumab group versus placebo group will be performed using Cochran-Mantel-Haenszel (CMH) test, stratified by vIGA-AD categories (moderate [vIGA-AD 3] vs. severe [vIGA-AD 4]). Point estimates and 95% CIs for the difference in proportions between each risankizumab group and placebo will be provided. Construction of CIs for the common risk difference will be based on the Mantel-Haenszel estimate adjusting for the stratification factor.

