### **8.2 Handling of Missing Data**

Missing data will be imputed using the following methods for the efficacy analyses:

- **Non-Responder Imputation** incorporating Multiple Imputation (MI) to handle missing data due to CCOVID-19 (NRI-C): the NRI-C analysis will categorize any subject who does not have evaluation during a pre-specified visit window (either due to missing assessment or due to early withdrawal from the study) as a non-responder for that visit. The exceptions are: 1) when the subject is a responder both before and after a specific visit window, in which case the subject will be categorized as a responder for the visit. (Only observations within the same analysis period will be used.) 2) missing data due to COVID-19 infection or logistical restriction will be handled by Multiple Imputation. In addition, all assessments after the start of rescue medications or prohibited medications will not be included in the analyses; as a result, subjects will be counted as non-responders thereafter and will not be imputed by MI. The NRI-C will be the primary approach in the analyses of categorical variables in Period A.

- A sensitivity analysis for categorical endpoints will use NRI with No special data handling for missing due to COVID-19 (NRI-NC). NRI-NC will be performed in the same way as NRI-C without the exception #2 above. That is, missing due to COVID-19 infection or logistical restriction will also be counted as non-responders. Subjects whose change/percent change from Baseline cannot be calculated because of a missing Baseline will be considered as a non-responder at all post-baseline visits in both NRI-C and NRI-NC approaches.
- Mixed-Effect Model Repeat Measurement (MMRM): The repeated measures analysis will be conducted using the mixed-effect model including observed measurements at all visits. The mixed-effect model includes the categorical fixed effects of treatment, visit and treatment-by-visit interaction, main stratification factors at randomization (vIGA-AD categories [moderate vs severe]), and the continuous fixed covariates of baseline measurement. An unstructured variance covariance matrix will be used. Parameter estimation is based on the assumption of data being missing at random and using the method of restrictive maximum likelihood (REML). The fixed effects will be used to report visit means at corresponding visits. MMRM will be the primary approach in the analysis of continuous variables in Period A.

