- Observed Cases (OC): The OC analysis will not impute values for missing evaluations, and thus a subject who does not have an evaluation on a scheduled visit will be excluded from the OC analysis for that visit. OC will exclude values after a subject prematurely discontinues from study drug. OC analysis will be used for the summaries of long-term efficacy for all variables in Period B.
- Multiple Imputation (MI): The MI approach will be used as a sensitivity analysis for the primary efficacy endpoint and the two key secondary efficacy endpoints. MCMC will be first applied to augment data into monotonic missing pattern and PROC MI will be used to generate 30 'complete' datasets using the regression method including the following variables in the imputation model: baseline value, treatment group, stratum (vIGA-AD categories [moderate vs severe]), and measurements at each visit up to the end of the analysis period. The seed for PROC MI will be set as the numeric form of the date when the 1st subject in this study is randomized. The imputed post-

baseline measurements will be rounded to the same precision as the observed data before the determination of responder status. Using the CMH model adjusted by stratification factor (vIGA-AD categories [moderate vs severe]), the imputed endpoints will be analyzed using each of the 30 datasets. SAS PROC MIANALYZE will be used to generate the final inferences of the risk difference between treatment groups.

In both Period A and Period B, efficacy assessments after the first dose of rescue or prohibited medication will not be included in the analyses for that period. As a result, after the first dose of rescue or prohibited medication, the subjects will be considered as non-responders in the NRI approach and will be considered as missing in OC and MMRM analyses.

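### Randomisation is stratified by vIGA-AD and by region (Japan or rest of world), but every efficacy model adjusts for vIGA-AD only and no reason is given

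*SAP*

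**What the plan says.** Both documents randomise on two factors. Baseline severity (vIGA-AD 3 or 4) is the first. The second is given in Protocol 5.8 as "and geographic region (Japan versus rest of world" and in SAP 2.3 as "and geographic region (Japan vs. Rest of the World [RoW". Region is not a token factor in this trial. The protocol synopsis states: "The study plans to enroll approximately 20% of subjects from sites in Japan".

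The efficacy analyses carry only the first factor:

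- **CMH test.** Protocol 7.3 has it "stratified by baseline disease severity (moderate [vIGA-AD 3] versus severe [vIGA-AD 4", and SAP 8.3.3 has it "using the CMH test adjusting for the stratification factor of vIGA-AD categories".
- **Risk difference.** SAP 8.1 states: "Construction of CIs for the common risk difference will be based on the Mantel-Haenszel estimate adjusting for the stratification factor". The factor is singular, and the same paragraph names it as vIGA-AD.
- **MMRM.** SAP 8.2 includes "main stratification factors at randomization (vIGA-AD categories [moderate vs severe". The wording is plural, but one factor is listed.
- **Multiple imputation.** SAP 8.2 includes "stratum (vIGA-AD categories [moderate vs severe]), and measurements at each visit up to the end of the analysis period".

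Region comes back only as a subgroup for the primary endpoint (SAP 8.6). SAP 8.3.4 plans no additional analyses of that endpoint, and no sensitivity analysis adds region.

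**The concern.** Stratified randomisation forces the arms to be balanced within each region. If response differs by region, that balance removes a source of chance variation from the treatment difference. An analysis that ignores region still counts that variation in its variance. The test then rejects less often than its nominal level allows, and some power is lost. Adjusting for the factors used in randomisation recovers the loss at almost no cost.

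The stake is a modest loss of power in a proof-of-concept trial with 31 placebo subjects, and a question the plan does not answer: why one randomisation factor was kept and the other dropped. Protocol 2.1 reports that the IL-23/Th17 pathway is more prominent in Asian patients. This does not show that region predicts EASI 75, but it makes an unexplained omission harder to defend.

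**Working it through.** **Inputs from the documents.** N = 155, allocated 2:2:1 (62/62/31). Two-sided alpha is 0.025 per dose. EASI 75 is at most 15% on placebo, with a difference of at least 36 points (Protocol 7.3, SAP 2.4). About 20% are from Japan, so 0.20 × 155 = 31 subjects, of whom 31/5 ≈ 6 are on placebo.

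**Stated power, reproduced.** Pooled rate = (31 × 0.15 + 62 × 0.51)/93 = 0.39. SE under the null = √[0.39 × 0.61 × (1/31 + 1/62)] = 0.1073. SE under the alternative = √[0.15 × 0.85/31 + 0.51 × 0.49/62] = 0.0902. Power = Φ[(0.36 − 2.241 × 0.1073)/0.0902] = Φ(1.32) = 90.7%. Exact enumeration of the chi-square test gives 91.0%. Both agree with the claim of more than 90%.

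**Test compared.** Within stratum k, x is the number of active responders, n1 and n0 the arm sizes, r the number of responders and n the stratum total:

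Q = [Σ(x − n1·r/n)]² / Σ[n1·n0·r·(n − r)/(n²(n − 1))]

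This was computed once over two vIGA-AD strata and once over four vIGA-AD × region strata.

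**Why the two-stratum test is conservative.** Take a region odds ratio of 4 and the moderate stratum, with null rates of 12.4% (rest of world) and 36.1% (Japan), chosen so that the overall rate is 15%. The stratum rate is 0.8 × 0.124 + 0.2 × 0.361 = 0.171.

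- Variance used when region is ignored: 0.171 × 0.829 = 0.142.
- Variance within regions: 0.8 × 0.124 × 0.876 + 0.2 × 0.361 × 0.639 = 0.133.
- Ratio: 1.07. The effective critical value is 2.241 × √1.07 ≈ 2.32, which gives a size of about 2.1% against the nominal 2.5%.

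**Simulation 1** (60,000 trials per scenario). Assumed: permuted blocks of 5 within the four strata; severity log-odds −0.7; severe share 50% in the rest of the world and 50% or 80% in Japan; the same region odds ratio in both arms; marginal rates held fixed. The table shows the power change in points from two to four strata. Ranges cover the two Japan severity shares.

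| Region odds ratio | 51% vs 15% | 40% vs 15% |
|---|---|---|
| 1 | −0.1 | −0.1 |
| 1.5 | +0.1 | 0.0 to +0.1 |
| 2 | +0.2 to +0.3 | +0.4 to +0.7 |
| 3 | +0.7 | +1.6 to +2.0 |
| 1/3 | +0.5 to +0.6 | +1.1 to +1.3 |
| 5 | +1.4 to +1.5 | +3.9 to +4.4 |

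Type I error was 1.9–2.4% with two strata and 2.3–2.4% with four. Coverage of the 95% Mantel-Haenszel interval (Sato variance) was 93.5–95.2% and 93.4–94.2%.

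**Simulation 2** (100,000 trials for size, 50,000 for power). Assumed: 45% severe, severity log-odds −0.4, blocks of 5; rates 51% vs 15%.

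| Region odds ratio | Type I error, two / four strata | Power, two / four strata |
|---|---|---|
| 1 | 2.28% / 2.27% | 91.0% / 90.9% |
| 2 | 2.29% / 2.37% | 91.1% / 91.4% |
| 4 | 1.99% / 2.32% | 91.9% / 93.1% |
| 8 | 1.52% / 2.34% | 92.4% / 94.7% |
| 1/2 | 2.31% / 2.36% | 91.1% / 91.4% |
| 1/4 | 2.28% / 2.41% | 91.5% / 92.5% |
| 1/8 | 2.13% / 2.35% | 91.6% / 93.2% |

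The 1.99% at an odds ratio of 4 agrees with the hand calculation of about 2.1%.

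**Sparse cells under the fix.** With Japan split 50/50 by severity, no simulated trial had a Japan cell without placebo subjects, and 34% had a cell with two or fewer. With 20% moderate and 80% severe, the figures are about 8% and 99%. Size and power still hold. As a further check at assumed placebo rates of 5%, 10% and 20% (50/50 split, odds ratios 1 to 5), four-stratum type I error was 1.7–2.4%, and power was never more than 0.1 point below the two-stratum test.

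**The case against.** The best defence is that this is a pre-specified choice on which protocol and SAP agree, so it leaves no analytic freedom after unblinding. Several further points are fair:

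- **Small gain at the planned effect.** A gain above 1 point at 51% versus 15% needs a region odds ratio of about 4 or more. The largest figures need both an odds ratio of 5 and a 25-point difference, neither of which is in the documents.
- **Region may modify the effect rather than predict outcome.** When region acts in the active arm only, power with two and four strata is 91.6% and 91.7% (odds ratio 2), 91.6% and 91.9% (3), and 91.8% and 91.9% (1/2).
- **Interval coverage.** It is slightly lower with four strata, by at most about 1 point.
- **Sparse cells.** About 6 Japanese placebo subjects would be a reasonable ground for using one factor.
- **Untested models.** Neither the MMRM nor the imputation model was simulated.

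These points limit the size of the matter but do not remove it. The sparse-cell reason is not stated anywhere, and thin cells damage neither size nor power. The coverage loss is small. The word "main" in the MMRM text is a label and does not explain the omission. What stands is that the gain may be close to nil and the current test is sound.

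**Conclusion.** The concern holds as a minor point. Two factors are used to randomise, one is used to analyse, and no reason is given. The planned CMH test is valid: simulated type I error never exceeded 2.5%, and power at the planned difference stays at about 91% or higher either way. No fault is claimed in the intervals.

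The possible loss is a fraction of a point of power for a region odds ratio up to 2 at the planned effect, about 1 point at 4, and about 4 points only if the odds ratio is near 5 and the true difference near 25 points. All of this rests on assumed region effects, severity effects and block size, with no missing data in Simulation 2. The documents give no response rates for vIGA-AD or pruritus, so no loss is claimed for the key secondary endpoints. The case for region in the MMRM and imputation models is consistency with the randomisation, not a simulated gain. The imputation model is spelled out only for the sensitivity analysis; that NRI-C uses the same one is inferred.

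**What to change.** In Protocol 7.3 and SAP 8.1 to 8.4, stratify the CMH test and the Mantel-Haenszel risk difference by vIGA-AD × region (four strata), and add region to the MMRM and imputation models. State in advance how a Japan cell with no subject in one arm is handled; in the CMH statistic such a cell contributes nothing.

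If vIGA-AD alone is kept, give the reason in one sentence and add the four-stratum CMH as a sensitivity analysis.

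The cost is wording plus one variable in the code, settled before the Week 16 blind break, by which time Protocol 7.1 requires the SAP to be final. Nothing changes for subjects or for site procedures. Changing Protocol 7.3 does require ethics committee review of the amendment (Protocol 8.1). The statistical costs are thin Japan placebo cells, slightly lower interval coverage and, if region has no effect, a power loss of about 0.1 point (at most 0.3 in any scenario run).

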## **2.4 Sample Size Determination**

Approximately 155 subjects will be randomized to risankizumab 150 mg, risankizumab 300 mg, or placebo in a ratio of 2:2:1 (62 subjects each for the risankizumab 150 mg and 300 mg groups and 31 subjects for the placebo group). Assuming an EASI 75 response rate of at most 15% in the placebo group, this sample size will provide more than 90% power to detect the treatment difference of at least 36% between each risankizumab group and placebo group using a two-sided test at a 0.025 significance level.

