### **Analysis of Continuous Variables**

The model based mean and standard error will be provided for continuous variables. The Baseline and visit means will also be presented for each treatment group among subjects who have both Baseline and at least one post Baseline visit values. Treatment groups will be compared using MMRM model as described in Section 8.2 with treatment, vIGA-AD categories and the corresponding baseline value in the model. Point estimates and 95% CIs of mean change from baseline within treatment groups, and between each risankizumab treatment group and placebo will be provided.

Unless otherwise specified, any subject who is randomized based on a wrong stratum will be analyzed according to the actual stratum the subject belongs to.

"Baseline" refers to the last non-missing observation before the first administration of study drug or randomization if no study drug is given.

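### The primary EASI 75 test is valid and meets its stated power, but adding baseline EASI is a cheap change that could gain a few points of power

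*SAP*

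**What the plan says.** The primary comparison is a pairwise CMH test of each dose against placebo, "using the CMH test adjusting for the stratification factor of vIGA-AD categories" (SAP 8.3.3). Protocol 7.3 agrees: the test is "stratified by baseline disease severity (moderate [vIGA-AD 3] versus severe [vIGA-AD 4". The stratum therefore has two levels.

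Baseline EASI is used elsewhere in the plan:
- For continuous endpoints, which include percent change in EASI, SAP 8.1 compares groups by MMRM "with treatment, vIGA-AD categories and the corresponding baseline value in the model".
- The multiple-imputation model in SAP 8.2 includes "baseline value, treatment group, stratum (vIGA-AD categories [moderate vs severe" categories), together with the visit measurements.
- SAP 8.6 lists a median split of baseline EASI as a subgroup factor for the primary endpoint, separately from baseline vIGA-AD.

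SAP 8.3.4 plans no additional analysis of the primary endpoint. SAP 8.3.2 names MMRM and MI as sensitivity analyses. However, SAP 8.2 defines MMRM for continuous variables, and the MI analysis ends in the same vIGA-AD CMH test. No planned test of EASI 75 adjusts for baseline EASI.

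**The concern.** Baseline EASI should be available for essentially every randomized subject: Protocol 5.1 requires EASI of at least 16 at Baseline, and the Activity Schedule has it at Day 0. The scale runs to 72, so subjects within one vIGA-AD category can still differ widely. The SAP carries both vIGA-AD and the baseline value in its other EASI models, so it already treats them as separate information.

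The stake is efficiency. Planned power is only just over 90%, with 31 placebo subjects and 0.025 per dose. Rejecting the primary hypothesis also releases alpha to the key secondary endpoints (SAP 12.0). If baseline EASI is prognostic within vIGA-AD categories, a test that uses it has more power from the same data.

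**Working it through.** **Inputs (SAP 2.4).** The arms are 62 and 31 per comparison. The placebo rate is from "Assuming an EASI 75 response rate of at most 15% in the placebo group". The effect is from "detect the treatment difference of at least 36" percentage points, so 51% versus 15%. The test is run "using a two-sided test at a 0.025 significance level", so z = 2.2414. The claim is that "this sample size will provide more than 90% power".

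**1. The plan's own figure.** Two-proportion formula, pooled variance under the null:
- Pooled rate = (31 × 0.15 + 62 × 0.51)/93 = 36.27/93 = 0.39.
- SE under the null = √[0.39 × 0.61 × (1/31 + 1/62)] = 0.1073.
- SE under the alternative = √[0.15 × 0.85/31 + 0.51 × 0.49/62] = 0.0902.
- Power = Φ[(0.36 − 2.2414 × 0.1073)/0.0902] = Φ(1.324) = **90.7%**.

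The stated power reproduces with no covariate.

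**2. Adding baseline EASI, by formula.** Let R² be the share of outcome variance that baseline EASI explains beyond vIGA-AD. Both SEs shrink by √(1 − R²). The documents give no R², so a range is assumed.

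| R² | Power, 36-point difference | Power, 25-point difference |
|---|---|---|
| 0 | 90.7% | 59.1% |
| 0.02 | 91.4% | 60.2% |
| 0.05 | 92.3% | 61.9% |
| 0.10 | 93.8% | 64.9% |
| 0.20 | 96.4% | 71.3% |

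At R² = 0.10, for example, Φ[(0.36/√0.9 − 0.2405)/0.0902] = Φ(1.54) = 93.8%. At the design effect the gain is 0 to 3.1 points for R² up to 0.10. In a simulation with equal severity strata, an odds ratio of 1.65 per SD of baseline EASI corresponded to R² of about 0.035, and 2.72 per SD to about 0.11.

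**3. Adding baseline EASI, by simulation.** A direct comparison of CMH with a logistic score test that includes EASI overstates what EASI contributes. With EASI not prognostic at all, the logistic test still came out ahead (91.2% versus 90.6% in one run, 91.0% versus 90.5% in another). A useless covariate cannot add power, so that difference comes from changing the statistic. A score test with vIGA-AD alone gave about 91.0% against 90.5% for CMH (20,000 trials, 40% assumed in vIGA-AD 4). The fair comparator is therefore the vIGA-AD-only score test. Net gain from EASI in points, from two separate simulations:

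| Log-odds slope per SD | 20,000-trial run | Second run |
|---|---|---|
| 0 | −0.2 | −0.3 |
| −0.3 | +0.3 | +0.4 |
| −0.6 | +1.8 | +2.0 |
| −1.0 | not run | +3.8 |

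**4. Test size (nominal 2.5%).** With both arms at 15%, the EASI-adjusted score test rejected in 2.6% to 2.9% of null trials. With both arms at 51% it rejected in 2.2% to 2.5%. A Wald test on the standardised risk difference rejected in up to 4.0%.

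**The case against.** The strongest reply is that nothing in the plan is wrong. The CMH test is valid, is specified the same way in Protocol 7.3 and SAP 8.3.3, and delivers its stated power. Adjusting for a randomization stratification factor is a standard choice that needs little defence. EASI 75 is already a percent change from each subject's own baseline, and vIGA-AD carries part of the same severity information. What baseline EASI still predicts within categories could be close to nothing. All of this stands, and it is why the point is labelled an improvement.

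The practical objections also carry weight. CMH fits no outcome model, while a logistic model would work with about 0.15 × 31 = 4.65 expected placebo responders. NRI-C uses multiple imputation for COVID-19-related gaps. The SAP's stated pooling route, PROC MIANALYZE on the risk difference, suits the Mantel-Haenszel estimate but does not directly cover a score test. These are reasons to specify the change carefully.

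The objection on test size does not defeat the score test, whose null rejection stays close to nominal. It does count against a Wald test on the standardised risk difference.

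**Conclusion.** The point holds as a low-cost efficiency suggestion. At the design effect the likely gain is roughly 0 to 3 points of power, reaching nearly 4 at a slope of −1.0 per SD. If baseline EASI is not prognostic, the cost is about 0.2 to 0.3 points. In relative terms the gain matters more if the true effect is smaller: at a 25-point difference and R² of 0.05 to 0.10, the formula gives 2.8 to 5.8 points. Every gain rests on an assumed prognostic strength that the documents do not supply.

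A reader might infer three stronger things that the documents do not support:
- **That the primary analysis is flawed or underpowered.** It is neither; 90.7% meets the stated target.
- **That power is certainly being lost, perhaps 6 or 7 points.** A gain of 6.7 points needs a partial correlation of 0.5, or 25% of the residual variance of a binary relative-change endpoint. Nothing in the documents supports that value.
- **That CMH buys nothing in return.** It avoids a fitted model where placebo responders are few.

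**What to change.** In SAP 8.3.3, with a matching line in Protocol 7.3, before the blind break:

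- Test EASI 75 for each dose by a logistic score test with treatment, vIGA-AD category and continuous baseline EASI.
- State how the test statistic is combined across the NRI-C imputed datasets.
- State a fallback to the vIGA-AD CMH test if the model fails to converge.
- Report the standardised risk difference for estimation only, not as a Wald test.
- Keep the vIGA-AD CMH test as a supportive analysis.

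No new data are needed. The cost is SAP and protocol wording, slightly more analysis work, and reliance on a model-based test with about 4.7 expected placebo responders.
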